## 6.4. Covariates and Subgroups

As a protocol defined exploratory analysis, HAI and Neut antibody response following vaccination will be summarized stratified by the following covariates: age (categorical: 19-35, 36-50, 51-70), sex (male, female), body mass index (<30, ≥30), and prior receipt of seasonal influenza vaccine(s) (receipt of 2017-2018 or 2018-2019, or receipt of neither), and these covariates will be considered in statistical modeling as described in Section 8.3. As these analyses are exploratory the study was not powered for any subgroup analyses.

## 6.5. Missing Data

All attempts will be made to collect all data Per-Protocol. As missing data are expected to be minimal, no imputation will be performed for missing values. Any data point that appears to be erroneous or inexplicable

based on clinical judgment will be investigated as a possible outlier. If data points are identified as outliers, sensitivity analyses will be performed to examine the impact of including or excluding the outliers. Any substantive differences in these analyses will be reported.

## **6.6. Interim Analyses and Data Monitoring**

Interim analyses will only be used to terminate this trial in the event that unanticipated safety events deemed to be of sufficient concern require such action by the sponsor. These assessments will not be made on the basis of testing a formal statistical hypothesis; therefore, p-value adjustment will not be made to any analyses. A DSMB will be convened by DMID to review study progress and participant, clinical, safety, and reactogenicity and immunogenicity data.

Clinical, safety, and reactogenicity data through approximately 365 days after study vaccination will represent the primary clinical database for this trial. Once the last subject completes the visit that occurs approximately 365 days after study vaccination and all HAI and Neut results are received, a “topline” subset of the immunogenicity and safety tables will be provided to DMID on an expedited timeline. These analyses may be made available to the sponsor for planning subsequent trials and to the lead PI for publication and will be considered the final analysis of these data.

Emergent public health needs may dictate additional interim safety, reactogenicity, and/or immunogenicity analyses be performed on available information at any time during the trial. If this occurs, immunogenicity data will be analyzed as results are available from the central immunogenicity laboratory.

### **6.6.1. Interim Safety Review**

An interim safety review may include enrollment and demographic information, medical history, concomitant medications, physical assessments, clinical laboratory values, dosing compliance, and solicited and unsolicited AE/SAEs. Additional data may be requested by the DSMB, and interim statistical reports may be generated as deemed necessary and appropriate by DMID. The DSMB may receive data in aggregate and presented by study arm. The DSMB may also be provided with expected and observed rates of the expected AEs in an unblinded fashion and may request the treatment assignment be unblinded for an individual subject if required for safety assessment. The DSMB will review grouped and unblinded data in the closed session only. The DSMB will meet and review this data at scheduled time points or ad hoc as needed during this trial as defined in the DSMB charter. As an outcome of each review/meeting, the DSMB will make a recommendation as to the advisability of proceeding with study vaccinations (as applicable), and to continue, modify, or terminate this trial. Summaries prepared for the DSMB are defined separately in a report shell reviewed and approved by the DSMB.

Additionally, this trial will be monitored to determine if any of the halting rules described in Protocol Section 9.5 are met.

### **6.6.2. Interim Immunogenicity Review**

There are no planned interim analyses for this study.

## **6.7. Multicenter Studies**

Although randomization was stratified by site, data will be pooled across all clinical sites for all analyses. Center effects are not anticipated because the sites are using standardized procedures for vaccination and assessment of solicited and unsolicited AEs, and the study relies on a central laboratory for immunogenicity assessments.

## **6.8. Multiple Comparisons/Multiplicity**

This study was designed to obtain preliminary estimates of safety and immune response to the A/H7N9 vaccination in healthy adults. The study was not designed to test any specific null hypothesis, and as such no adjustment for multiple comparisons will be performed.

---

## 7. STUDY SUBJECTS

### 7.1. Disposition of Subjects

[Table 13](#) will present a summary of the reasons that subjects were screened but not enrolled.

The disposition of subjects in the study will be tabulated by study group and stratum in [Table 14](#). The table will show the total number of subjects screened, randomized, receiving the study vaccination, completing the blood draw for the primary immunogenicity endpoints, and completing the last visit.

The number and percentage of enrolled subjects excluded from each analysis population by study group and stratum are presented in [Table 15](#). A listing of subjects excluded from each analysis population will be presented in [Listing 5](#).

A flowchart showing the disposition of study subjects, adapted from the CONSORT Statement [4] will be included and will present the number of subjects screened, randomized, lost to follow up, and analyzed, by study group and stratum in [Figure 1](#).

A listing of subjects who terminated early from study follow up and the reason will be included in [Listing 2](#).

### 7.2. Protocol Deviations

A summary of subject specific protocol deviations will be presented by the deviation category and deviation type, study group, and stratum for all enrolled subjects in [Table 8](#). Major deviations that will be reviewed for possible exclusion of immunogenicity results from the PP population include deviations related to eligibility/enrollment, follow-up visit schedule, and receipt of exclusionary vaccines or medications. All subject-specific protocol deviations and non-subject-specific protocol deviations will be included in [Listing 3](#) and [Listing 4](#).

## 8. IMMUNOGENICITY EVALUATION

Analysis of all immune responses will be conducted using the PP population. In addition, primary endpoint analyses will be conducted with the mITT population. Immune responses in terms of strain-specific A/H7N9 HAI and Neut antibody titers will be summarized by study group at each time point. Descriptive summary statistics will be provided for all assays and time points including number of subjects with non-missing results, percentage of subjects with titers  $\geq 40$ , percentage of subjects achieving seroconversion, and GMTs along with corresponding 95% CIs. Exact CIs will be presented for proportional endpoints. Summaries of primary and secondary immunogenicity endpoints are presented in [Table 22](#), [Table 23](#), [Table 24](#), and [Table 25](#).

Reverse cumulative distribution (RCD) curves will be presented for HAI and Neut antibody titers against A/Hong Kong/125/2017 (H7N9), A/Shanghai/2/2013 (H7N9), and A/Guangdong/17SF003/2016 (H7N9) strains. Plots for each assay will be generated with 4 panels (pre-vaccination, 7 days post vaccination, 21 days post vaccination, and 180 days post vaccination) and separate curves within each panel for each study group and stratum, as shown in [Figure 2](#), [Figure 3](#), [Figure 4](#), [Figure 5](#), [Figure 6](#), [Figure 7](#), [Figure 8](#), and [Figure 9](#).

HAI and Neut antibody GMTs against A/Hong Kong/125/2017 (H7N9), A/Shanghai/2/2013 (H7N9), and A/Guangdong/17SF003/2016 (H7N9) will be presented graphically with corresponding 95% CIs in [Figure 10](#), [Figure 11](#), [Figure 12](#), [Figure 13](#), [Figure 14](#), [Figure 15](#), [Figure 16](#), and [Figure 17](#).

The spearman correlation between HAI and Neut antibody titers will be calculated at each time point over all stratum and group combinations for each strain. The correlation will be depicted in scatterplots as depicted in [Figure 18](#), [Figure 19](#), [Figure 20](#), and [Figure 21](#).

Individual HAI and Neut assay results will be provided in [Listing 9](#) and [Listing 10](#), respectively.

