11.6.3 Immunogenicity Data

Summaries and analysis of immunogenicity data will be presented for the mITT and PP populations.

Immune responses in terms of strain-specific 2013 and 2017 A/H7N9 HAI and Neut antibody titers will be summarized by treatment arm at each time point. Analyses will include number and percentage of subjects with a titer $\geq 1:40$, number and percentage of subjects achieving seroconversion (defined as either a pre-vaccination titer $< 1:10$ and a post-vaccination titer $\geq 1:40$ or a pre-vaccination titer $\geq 1:10$ and a minimum four-fold rise in post-vaccination antibody titer), and GMTs along with corresponding 95% CIs. Descriptive summary statistics will be provided for all assays and time points. The correlation between HAI and Neut antibody titers will be evaluated. Plots such as reverse cumulative distributions or longitudinal presentations of GMTs will be presented.

Additionally, the immune response, as described above, will be summarized by available covariates, such as age, sex, BMI, and prior receipt of seasonal or non-study pandemic influenza vaccine(s), and these covariates may be considered statistical modeling. As an exploratory analysis, models may be developed to evaluate the relationship between use of adjuvant and

prime and/or boost regimens with the elicited immune response. For example, logistic regression may be used to examine the relationship of proportion of responders with adjuvant use in the prime and/or boost regimens and available covariates may be considered for inclusion in the model.

At least a subset of samples will also be tested for cross-reactive serum HAI and Neut antibody responses to antigenically drifted variants of influenza A/H7 viruses. Strain-specific results will be summarized using descriptive statistics as described above, correlations with 2013 and 2017 A/H7N9 responses and association with adjuvant use in the prime and/or boost regimens.

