### 4.4.3. Method of Assigning Subjects to Treatment Groups (Randomization)

Enrollment/randomization will be performed through the enrollment module in the electronic data capture system maintained by the Statistical and Data Coordinating Center (SDCC).

Eligible subjects will be stratified by prior receipt of 2013 A/H7N9 IIV with or without adjuvants, clinical site, and prior receipt of licensed, seasonal influenza vaccine then randomly assigned with allocation (1:1) to one of two treatment arms to receive 1 dose of 2017 A/H7N9 IIV at 3.75 mcg HA per dose with or without AS03 adjuvant. There is a total of ten strata with maximum enrollments outlined in [Table 1](#).

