## 5. SAMPLE SIZE CONSIDERATIONS

This study is planned to enroll up to 420 subjects. The majority of subjects will be recruited from the population of subjects who received the 2013 A/H7N9 IIV in DMID Protocols 13-0032 and 13-0033. The sample size for this study was selected using estimates of recruitment based on the number of subjects completing these historical protocols and by 2013 A/H7N9 IIV vaccination history. [Table 4](#) summarizes the vaccination history in these protocols and potential enrollment into this study. While this study is not designed to test any specific null hypothesis, the following tables illustrate the precision and power that is available for select estimates and comparisons of interest.

[Table 5](#) indicates the probability of observing one or more safety events, such as solicited injection site or systemic reactogenicity events or an unsolicited non-serious AE of a particular type for treatment arms (N=30, 50), in all subjects receiving adjuvant (N=210) or in the trial as a whole (N=420).

Binomial confidence intervals (CIs) are widest (have the least precision) when the response rate is 50%. [Table 6](#) is presented to indicate the worst-case scenario for precision of observed exact (Clopper-Pearson) binomial confidence intervals.

[Table 7](#) illustrates the minimum detectable differences in the proportion of subjects responding (e.g. attaining seroconversion or a titer  $\geq 40$ ) between any two treatment arms (N=30 or 50) using a two-sided Likelihood Ratio Test with  $\alpha = 0.05$ . From previous experience with single dose studies, it is assumed that up to 3% of subjects will be excluded from the per protocol analysis with minimal effect on these calculations. Seroconversion rates of 10% to 90% are considered.

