[Implementation Note: A generic sample figure is shown below. The scatter plots should be presented in a single figure with separate panels for each visit (Day 1, Day 8, Day 22, D181). Visit labels should be included in the panel header. Within each panel distinct marker types and colors should be used to indicate the treatment arms, with treatment group labels included in a legend. Each treatment arm should have a separate color, with marker shape used to distinguish strata. The spearman correlation should be calculated over all subjects and annotated within each panel as “Spearman Correlation (r=0.xx, p=0.xx)”]

Figures with similar format:

- Figure 19:** Correlation of Hemagglutination Inhibition Antibody and Neutralizing Antibody Against A/Hong Kong/125/2017 (H7N9) by Study Day, Stratum and Study Group, Per-Protocol Population
- Figure 20:** Correlation of Hemagglutination Inhibition Antibody and Neutralizing Antibody Against A/Shanghai/2/2013 (H7N9) by Study Day, Stratum and Study Group, Per-Protocol Population
- Figure 21:** Correlation of Hemagglutination Inhibition Antibody and Neutralizing Antibody Against A/Guangdong/17F003/2016 (H7N9) by Study Day, Stratum and Study Group, Per-Protocol Population
- Figure 22:** Correlation of A/Hong Kong/125/2017 (H7N9) and A/Shanghai/2/2013 (H7N9) Hemagglutination Inhibition Antibody Results by Study Day, Stratum and Study Group, Per-Protocol Population
- Figure 23:** Correlation of A/Hong Kong/125/2017 (H7N9) and A/Shanghai/2/2013 (H7N9) Neutralizing Antibody Results by Study Day, Stratum and Study Group, Per-Protocol Population
- Figure 24:** Correlation of A/Hong Kong/125/2017 (H7N9) and A/Guangdong/17F003/2016 (H7N9) Hemagglutination Inhibition Antibody Results by Study Day, Stratum and Study Group, Per-Protocol Population
- Figure 25:** Correlation of A/Hong Kong/125/2017 (H7N9) and A/Guangdong/17F003/2016 (H7N9) Neutralizing Antibody Results by Study Day, Stratum and Study Group, Per-Protocol Population

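### The Spearman correlations printed in SAP Figures 18-25 pool all ten groups, so r and p mix between-group with within-group association; a group-adjusted coefficient with a CI should be added and the p-value dropped

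*SAP*

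**What the plan says.** SAP section 8 plans the Spearman correlation between HAI and Neut titers to be "calculated at each time point over all stratum and group combinations for each strain", with scatterplots in Figures 18 to 21. The implementation note for Figure 18 (SAP Appendix 2, 14.2.2) repeats the rule: "The spearman correlation should be calculated over all subjects and annotated within each panel". The annotation template is "Spearman Correlation (r=0.xx, p=0.xx" (closing bracket left off here), so a p-value accompanies each coefficient.

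Figures 19 to 25 are listed as having the same format. Figures 22 to 25 plot the vaccine strain against a heterologous strain within one assay (SAP 8.3.3), so they take over the same pooled annotation.

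The figure titles name stratum and study group, but grouping enters only through the plotting symbols: "Within each panel distinct marker types and colors should be used to indicate the treatment arms", with marker shape separating the strata. Neither document plans a within-group, stratified or partial coefficient. Protocol 11.6.3 states the aim in one sentence: "The correlation between HAI and Neut antibody titers will be evaluated".

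**The concern.** The ten groups are two arms (with or without AS03) crossed with five priming histories (SAP Table 1). The design expects these factors to move titers. Protocol 2.1 cites large antibody increases with oil-in-water adjuvants, and Protocol 11.1 gives evaluation of the priming effect as the reason for these arms. HAI and Neut are measured on the same subjects' sera, so a factor that raises both adds covariance between groups to any pooled coefficient.

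The annotated r then answers a mixed question: how closely the titers move together across this particular blend of groups, with its planned sizes of 50 and 30. It does not isolate how closely they move together among subjects with the same vaccine history. A reader cannot separate the two from the annotation. A small p-value could appear with no association within any group.

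**Working it through.** **1. The plan's own figure.** Neither document states a value for the correlation. The nearest usable figure is SAP Table 7, N=50 per arm, 0.20 vs 0.46 responders, 80% power by a two-sided likelihood ratio test at alpha 0.05. Exact binomial enumeration of that test gives 0.801, and the pooled z approximation gives 0.799, so the row reproduces. It serves here only to set the size of a group difference that the design treats as detectable.

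Group sizes are 6 × 50 + 4 × 30 = 420, matching "This study is planned to enroll up to 420 subjects". Subjects are "randomly assigned with allocation (1:1) to one of two treatment arms", so 210 fall in each arm.

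**2. Responder rates converted to a shift in SD units.** Assume normal log titers with a common SD, and response meaning a titer of at least 40. Then d = Φ⁻¹(higher rate) − Φ⁻¹(lower rate).

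- 0.20 vs 0.46: −0.100 + 0.842 gives d = 0.741
- 0.10 vs 0.50: 0 + 1.282 gives d = 1.282
- 0.10 vs 0.90: 1.282 + 1.282 gives d = 2.563

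**3. Closed form with zero within-group correlation.** For two equal arms and the same shift d on both assays, the between-arm covariance is d²/4 and the total variance is 1 + d²/4. The pooled Pearson correlation is therefore r = (d²/4) / (1 + d²/4).

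- d = 0.741: 0.137 / 1.137 = 0.12
- d = 1.282: 0.411 / 1.411 = 0.29
- d = 2.563: 1.642 / 2.642 = 0.62

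**4. Simulation with the assay's ties and floor.** There were 600 runs per scenario with the ten planned group sizes. Log2 titers were bivariate normal with SD 1.5 (assumed), reduced to two-fold steps, with values below 10 set to 5 as in SAP 4.5.2. One reading per sample was used. The within-group r is the mean of the ten group coefficients weighted by n − 1. Latent rho is the correlation before rounding and flooring.

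| Assumed group difference | Latent rho | Pooled r | Within-group r | Pooled p<0.05 |
|---|---|---|---|---|
| None | 0 | 0.00 | 0.00 | 5% |
| Arms 0.20 vs 0.46 | 0 | 0.12 | 0.00 | 69% |
| Same, plus equal shift for all primed strata | 0 | 0.16 | 0.00 | 92% |
| Arms 0.10 vs 0.50 | 0 | 0.29 | about 0.00 | 100% |
| Arms 0.10 vs 0.90 | 0 | 0.65 | 0.00 | 100% |
| None | 0.6 | 0.54 | 0.53 | 100% |
| Arms 0.20 vs 0.46 | 0.6 | 0.60 | 0.54 | 100% |
| Arms 0.10 vs 0.50 | 0.6 | 0.67 | 0.53 | 100% |
| Arms 0.10 vs 0.90 | 0.6 | 0.84 | 0.53 | 100% |
| Arms 0.20 vs 0.46 | 0.8 | 0.78 | 0.74 | 100% |

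With rho = 0, a z test on the within-group coefficient gave p<0.05 in about 4 to 7% of runs in every scenario, close to nominal.

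**5. Which panels are exposed.** The Figure 18 note calls for panels at Day 1, Day 8, Day 22 and Day 181. At Day 1 no study vaccine has been given and the arms are randomized within stratum, so AS03 cannot separate them. Only priming history can contribute there.

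**The case against.** The strongest reply is that the pooled coefficient is a valid description of association across the enrolled sample, which is all that Protocol 11.6.3 asks for. The points are coded by arm and stratum, and individual titers are listed (Listings 9 and 10), so the within-group pattern is partly visible. SAP 8.1 and 8.3.3 plan no formal testing for the primary summaries or the heterologous strains, and no decision uses these figures. All of this stands, and it keeps the point minor.

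The size is also conditional. If the assays correlate strongly within groups and the groups differ modestly, the inflation is about 0.04 to 0.07. That stands too.

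Three stronger readings go further than the documents allow:

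- A reader might infer that the plan offers the coefficient as evidence of assay agreement. Neither document says so, and no Spearman coefficient, pooled or within-group, measures agreement.
- A reader might infer that the p-value tests the group difference. It tests zero association in the pooled sample. Group differences alone drive it only when within-group association is absent.
- A reader might want ten separate coefficients in every panel. At 30 to 50 subjects each they would be imprecise, and any group whose titers all sit at the floor would have none.

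The reply leaves one thing unanswered: the single number printed in each panel cannot be split into its two sources.

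**Conclusion.** The point holds as a minor reporting improvement. After vaccination the pooled r and p combine between-group and within-group association, and the plan provides nothing to separate them. The effect runs from small (0.60 vs 0.54 at latent rho 0.6 with a Table 7 difference between arms) to large (0.84 vs 0.53 when the arms are far apart). With no within-group association, the pooled r is about 0.12 to 0.29 for the two more moderate arm differences considered, and p is below 0.05 in 69% to 100% of runs.

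These values rest on an assumed SD of 1.5 log2, assumed latent correlations, and equal shifts on both assays. The documents give none of these. They show what can happen, not what the trial's data will show.

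**What to change.** In SAP section 8 and the Figure 18 note, with Figures 19 to 25 following:

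- Report in each panel a group-adjusted Spearman with a 95% CI. It can be a partial Spearman given the ten stratum-by-arm groups, or the size-weighted within-group mean r_w = Σ(n_g − 1)r_g / Σ(n_g − 1). Name one in the SAP, and omit any group with no titer variation, stating how many were omitted.
- Keep the pooled r, labelled as pooled over all groups.
- Drop the p-value, in line with SAP 8.1 and 8.3.3.

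Precision is adequate. Near zero association, with all ten groups contributing, the weights sum to 420 − 10 = 410, so the CI half-width is about 1.96 / √410 = 0.10.

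The cost is slightly more programming and a revised annotation, on data already collected. The adjusted coefficient will usually be lower than the pooled one, which the text should explain.

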### 8.1. Primary Immunogenicity Analysis

The primary immunogenicity endpoints of HAI and Neut seroconversion, percentage of subjects with titer  $\geq 40$ , and GMTs against the homologous A/H7N9 vaccine strain 21 days after study vaccination will be summarized as described above. Regression modeling of seroconversion and log titers is planned as described in Section 8.3.2. No formal hypothesis testing is planned.

### 8.2. Secondary Immunogenicity Analyses

The secondary immunogenicity endpoints of HAI and Neut seroconversion, percentage of subjects with titer  $\geq 40$ , and GMTs against the homologous A/H7N9 vaccine strain 7 and 180 days after study vaccination and the 2013 A/H7N9 vaccine strain 21 days after study vaccination will be summarized as described above.

### 8.3. Exploratory Immunogenicity Analyses

Immunogenicity data summaries and analysis for exploratory endpoints will be presented for the PP populations.

#### 8.3.1. Covariate Analysis

As an exploratory analysis, seroconversion and GMT of HAI and Neut antibodies against A/Hong Kong/125/2017 (H7N9) at 21 days post study vaccination will be summarized by study group, and stratified by prior receipt of 2013 A/H7N9 influenza vaccine in [Table 26](#) and [Table 27](#); by stratum and age (categorized as those subjects ages 19-35, 35-50, 51-70) in [Table 28](#) and [Table 29](#); by sex in [Table 30](#) and [Table 31](#); by

stratum and BMI in [Table 32](#) and [Table 33](#); and by stratum and prior receipt of seasonal influenza vaccines in [Table 34](#) and [Table 35](#).

